15.1.2 Missing Data Methods for Primary Analysis Variable

Multiple imputation technique will be used to address missing values for primary endpoint in case of percentage of missing data will be $\geq 20\%$. Multiple imputation it's superior to single imputation in reducing statistical bias by building in random error into the imputation. This prevents underestimation of the degree of variability in the data, which affects the estimate of the standard error.

Document:	Y:\Kimberly-Clark\DryNites\Documentation\SAP\DryNites_SAP_v1.0_20200203		
Author:	[name]	Version Number:	1.0
		Version Date:	03Feb2020
Template No.:	RWI_TP_BIOS0013 Revision 1	I	Reference: RWI_WI_BIOS0015
Effective Date:	15Jun2018		

The following steps will be used:

- Differences on all key and outcome variables between patients with missing versus nonmissing values will be described and tabulated.
- Missing data will be imputed using SAS PROC MI under the assumption that the missing values are missing at random (MAR). This assumption requires that missing values be related to measured covariates, with no unmeasured related covariates.
- Results will be aggregated across the multiply imputed data sets using SAS PROC MIANALYZE.

The multiple imputation model will include the primary outcome as the number of wet nights during the last week on the 4 weeks period after randomisation, randomisation group, average number of wet nights during the run-in period, age and sex. The number of imputation data sets to be created is 100.

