#### 4.7.2. Direct-to-Patient Data Collection

The following data will be collected daily for all enrolled patients using an electronic diary from the morning following the baseline visit until discontinuation from the study:

- Were absorbent pants worn? Yes/No/Another brand
- Was the bed mat used? Yes/No/Another brand
- Did the child have an NE event? Yes/No
- How was the NE event managed? One response to be selected: Child slept through the night; child awoke but did not take any action; child awoke and changed pants/changed bed/visited toilet but did not disturb parents; child awoke and woke parents.

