8.3 Missing Data

Should missing data occur, the data will be analysed as recorded in the electronic CRF (eCRF), that is, analyses will be performed on patients with non-missing values. However, the amount of missing values for data elements will be reported, and the likely impact of missing data on the analysis and the pattern of the missing information will be assessed.

Depending upon the amount of missing data, and whether there is evidence of bias in the missing data (e.g., differences between patients with and without missing data), multiple imputation (detailed in Section 15.1.2), may be performed and a sensitivity analysis will be carried out comparing the results from the complete case analysis (where records with missing data will be dropped) and the full set analysis including the imputed data.

Missing safety data will not be imputed. Partial date handling is described in Appendix 2.

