15.1.4 Sensitivity Analysis of Primary Variable

The sensitivity analysis will be performed as described in Section 15.1.2 in case of observing 20% or more of the missing date for the primary variable. Descriptive statistics for the analysis population will be computed comparing the original values to the imputed values.

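### The imputation model for a missing Week 4 leaves out the child's Week 1–3 diary and its fixed 20% trigger can go unmet, so it would correct almost none of the bias if loss depends on the course after randomisation

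*SAP*

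**What the plan says.** SAP 15.1.2 sets the rule: "Multiple imputation technique will be used to address missing values for primary endpoint in case of percentage of missing data will be" at least 20%. Imputation uses PROC MI under missing at random. Besides the Week 4 count, the model holds "randomisation group, average number of wet nights during the run-in period, age and sex". "The number of imputation data sets to be created is 100". No diary variable from the intervention period is listed.

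SAP 15.1.4 repeats the threshold, "in case of observing 20% or more of the missing date for the primary variable", and calls the result a sensitivity analysis. Neither section says whether the 20% is overall or by arm, or whether it counts children or nights.

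SAP 8.3 gives a different rule. By default "analyses will be performed on patients with non-missing values". Imputation may be done "Depending upon the amount of missing data, and whether there is evidence of bias in the missing data", with no percentage, and its results are compared with complete case. Protocol 5.4.5 says much the same.

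On the diary, Protocol 4.7.2 says: "The following data will be collected daily for all enrolled patients using an electronic diary", from the morning after the baseline visit until discontinuation. Protocol 4.3.6 keeps data collected before a withdrawal for analysis. Protocol 4.3.1 requires 7 wet nights in the last run-in week for randomisation and, at enrolment, on average no more than one dry night a month over six months.

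**The concern.** Missing at random is only as credible as the variables in the model. Here the one outcome-related covariate, the run-in average, has been squeezed by eligibility to near its ceiling. The best available predictor of a child's Week 4 is that child's own Weeks 1–3, which the trial collects.

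The trial is open-label and one arm has its pants removed, so families may stop recording or withdraw in response to what they see in those weeks. Protocol 5.4.6 itself expects that missing diary data may be substantial. If loss follows the early course, the listed model has nothing with which to correct it. In an equivalence trial the case that matters most is loss of the drier no-pants children, because that shrinks the difference. A single overall trigger in a 2:1 trial can also leave heavy one-sided loss unadjusted.

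**Working it through.** **Inputs from the documents.** Wet-night rates 0.95 (continue) and 0.80 (discontinue), margin 2/7, 15 continuing children per age group, 2:1 allocation, 120 children (Protocol 5.1, 5.2). At 2:1, 120 children are 40 and 80.

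**1. The plan's own figure.** Drawing Binomial(7, p) counts for 15 and 30 children and asking whether the 95% Wald interval for the risk difference lies inside ±2/7 gives power 97.8%, against 99% stated. That is close enough to use the planning rates here. The planned difference is 7 × (0.95 − 0.80) = 1.05 nights. The margin is 2 nights, which leaves 2 − 1.05 = 0.95.

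**2. The trigger.** With 25% missing in the no-pants arm and 5% in the other: (0.25 × 80 + 0.05 × 40)/120 = 22/120 = 18.3%. No imputation is triggered. With 5% missing in the continuing arm, the no-pants arm must reach (24 − 2)/80 = 27.5% before the overall figure is 20%.

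**3. Why the model returns complete case.** Within an arm, the average imputed value is roughly the observed mean + b × (covariate mean among missing − covariate mean among observed). If the covariate barely varies or barely predicts, the second term is near zero and the complete-case mean remains.

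**4. Simulation, loss related to Weeks 1–3.** Assumed, not in the documents: each child has a persistent rate (beta-binomial, within-child correlation 0.2 or 0.4). All losses fall in the no-pants arm, and the log-odds of loss change by 1 per wet night in Weeks 1–3. There were 1,500 data sets per scenario. At 20% missing, 24 of 80 no-pants children (30%) are lost. The difference is continuing minus discontinuing.

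| Loss, 20% overall | Bias, complete case | Bias, SAP model | Bias, Weeks 1–3 added (by arm) |
|---|---|---|---|
| Random | 0.00 | 0.00 | 0.00 |
| Wetter leave | +0.30 to +0.44 | +0.30 to +0.44 | 0.00 |
| Drier leave | −0.47 to −0.80 | −0.47 to −0.80 | within 0.01 of zero |

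- With half that log-odds slope, the bias when wetter children leave is +0.20 to +0.33.
- At about 19% missing the SAP imputation does not run, and the complete-case bias when wetter children leave is +0.29 to +0.42.
- If the run-in average is allowed to predict later wetting within the eligible range, the SAP model removes only about a tenth of the bias when wetter children leave (+0.30 to +0.27; +0.44 to +0.39).

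**5. Milder loss.** Assume 35% loss among no-pants children averaging 6 or more wet nights early on (or, reversed, fewer than 6), and 5% among all others. The SAP model again matches complete case: 1.21 to 1.31 if wetter children leave and 0.82 to 0.88 if drier ones do, against a truth of 1.05. These are shifts of about +0.16 to +0.26 and −0.17 to −0.23. Adding Weeks 1–3 gives 1.04 to 1.06. Overall missing is 12–18%, so the trigger is met in only 1–28% of runs.

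**6. Loss related to Week 4 itself.** Assume 35% loss if the no-pants child has 5 or fewer wet nights in Week 4, otherwise 5%. Complete case gives 0.82 and 0.76 (correlation 0.2 and 0.4). Regression imputation using Weeks 1–3 gives 0.94 and 0.98. The correction is only partial.

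**The case against.** - **The bias is conditional.** A reader might infer that the primary estimate is biased. The documents do not support that: they give no dropout mechanism and no rate by arm. The bias is zero if loss is random or if children do not differ in underlying rate. This stands.
- **Differential loss would be seen.** A reader might also infer that the plan could not detect it. That is wrong. SAP 15.1.2 first tabulates children with and without missing values on key and outcome variables, SAP 8.3 requires the pattern and likely impact to be assessed, and SAP 15 summarises diary data on both the randomised and primary sets. These steps can show the problem but do not correct it.
- **20% is not the only rule.** SAP 8.3 would allow imputation on evidence of bias below 20%. So the defect is a conflict between sections as well as a fixed threshold.
- **The role of imputation is mostly settled.** SAP 8.3 and 15.1.4 describe a sensitivity comparison. Only the opening of 15.1.2 reads otherwise.
- **The simulation favours the fix.** Loss was generated from early weeks and early weeks were then added, so full recovery in steps 4 and 5 is built in. Step 6 shows the limit.
- **One direction is conservative.** If wetter children leave, the estimate moves away from equivalence. At a true difference of 2 nights, false equivalence falls to roughly 0.3–0.4%, from about 2.3% with full data. With drier children leaving (35% against 5%) it rises to roughly 10–16%. The risk to the trial's claim lies in that second case.

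**Conclusion.** The point holds in conditional form. The listed covariates make the planned imputation nearly a copy of complete case, and the fixed trigger may keep it from running at all. If loss of Week 4 follows the child's course after randomisation, both estimates are off by about +0.2 to +0.4 nights (wetter children leave) or −0.2 to −0.8 (drier children leave). The larger shifts toward equivalence, 0.47 to 0.80, are 49% to 84% of the 0.95 nights between the planned difference and the margin.

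Size and sign rest on the assumed loss patterns, on losses falling wholly or mainly in the no-pants arm, and on a within-child correlation of 0.2 to 0.4. That such loss is plausible in an open-label trial is a judgement; the documents do not show that it will occur. The omission of Weeks 1–3, the trigger arithmetic and the conflict with SAP 8.3 need no such assumption.

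**What to change.** - **Model (15.1.2).** Add wet-night counts or proportions for intervention Weeks 1, 2 and 3, by arm, to the PROC MI model.
- **Trigger (15.1.2, 15.1.4, 8.3).** Replace the 20% threshold with imputation whenever any Week 4 value is missing, and align 8.3 with it.
- **Role (15.1.2).** State, as 15.1.4 and 8.3 already do, that this is the sensitivity analysis to the complete-case primary estimate.
- **Departure from missing at random.** Add a simple delta check that shifts the imputed values, because Weeks 1–3 only partly correct loss that depends on Week 4 itself.

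Predictive mean matching, to keep imputed counts between 0 and 7, is optional. The SAP names no imputation method, and out-of-range values were not shown to bias the difference.

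The cost is SAP wording and a little extra analysis code. The data are already collected, and under random loss the larger model introduced no bias.

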## 5.2. Sample Size

The sample size calculation is based on simulations according to the following procedure: During the 4-week trial period, there will be twice as many children assigned to the intervention group (discontinuation of absorbent pants) compared with the control group (continued use of DryNites®). For each child in the 2 groups, the number of wet nights during the last week is simulated from a binomial distribution with n=7 as the number of trials and probabilities  $p_0$ =0.95 and  $p_1$ =0.80 indicating the risk of a wet night in the control group and intervention group respectively. The simulations are conducted for various sample sizes, each with 1000 simulated data sets. For each data set the risk difference ( $p_0$ - $p_1$ ) is estimated with a corresponding 95% confidence interval (CI). The 2 methods are said to be equivalent with an equivalence margin  $\delta$  if CI of the risk difference lies within the interval [- $\delta$ ,  $\delta$ ]. This is done for different values of  $\delta$ , here for  $\delta$ =2/7, 3/7, 4/7 corresponding to 2, 3 and 4 dry nights per week (i.e., 5, 4, and 3 wet nights per week). Finally, the power for each sample size is calculated as the number of estimates with a CI lying within the defined interval [- $\delta$ ,  $\delta$ ] out of the 1000 simulations.

Fifteen participants are needed in the continuation arm to obtain a power of 99%. This means that a total of 3x15=45 participants are needed at randomisation (due to the 2:1 randomisation). Fifteen additional participants are added to this number (total of 60 participants) to compensate for dropouts/poor compliance during the trial, and for the participants who will be excluded at randomisation because they did not fulfil the criteria of 7 wet nights per week (screen failures). Additionally, the primary endpoint will be analysed separately for the 2 age groups (4–<6 and  $\geq$ 6–8 years of age) and therefore 60 participants will be needed for each age group (total 120 participants).

The same simulations have been performed with different definitions of equivalence, i.e., 5, 4, and 3 wet nights per week and this showed approximately the same number of participants needed for obtaining 100% power. Similarly, if the assumption of 15% reduction in the control arm is changed to 20% it does not change the conclusions either.

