15.1 Primary Analysis

The primary analysis will be performed separately for age groups for the PAS comparing the 95% CI for the difference between the means of average wet nights at the end of intervention period for the 2 groups with the predefined margin. Being the primary analysis focused on last week of the intervention period (lasting from randomisation to Visit 3) and the equivalence margin reported as 2/7 (two nights over a week), the average number of wet nights was chosen as reliable outcome on primary endpoint.

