15.1.3 Primary Analysis of Primary Variable

The primary objective of this study is to demonstrate if discontinuation of nocturnal use of absorbent pants in children with NE has any impact on the rate of spontaneous resolution of NE, compared with continued use of absorbent pants, over a period of 4 weeks.

The primary effectiveness analysis will be performed for the PAS comparing the 95% CI for the difference between the means of average wet nights at the end of intervention period for the 2 groups with the predefined margin ($\delta = 2/7$). If the CI lies strictly within [- δ , + δ], the study hypothesis will be demonstrated. Difference in means and CI will be generated by PROC TTEST for independent groups.

Primary analysis will be also repeated by age groups (4–<6 years and \geq 6–8 years).

Document:	Y:\Kimberly-Clark\DryNites\Documentation\SAP\DryNites_SAP_v1.0_20200203		
Author:	[name]	Version Number:	1.0
		Version Date:	03Feb2020
Template No.: F	RWI_TP_BIOS0013 Revision 1		Reference: RWI_WI_BIOS0015
Effective Date:	15Jun2018		

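### The SAP's imputation model has no age-stratum-by-arm term, so if imputation is triggered and the arm effect differs by age, each age group's imputed estimate is pulled towards the other's

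*SAP*

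**What the plan says.** SAP 15.1.2 provides for multiple imputation of the primary outcome with PROC MI under a missing-at-random assumption, using 100 data sets. The model contains the Week 4 wet-night count, "randomisation group, average number of wet nights during the run-in period, age and sex". Age is named, but not the randomisation stratum. No interaction is listed, no PROC MI method is named, and nothing says that imputation is done separately by age group.

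The trigger appears in SAP 15.1.2 as 20% or more missing. SAP 15.1.4, headed as a sensitivity analysis, repeats it: "in case of observing 20% or more of the missing date for the primary variable". Neither section says whether the percentage is counted overall or per age group.

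On the comparison that these data sets feed:
- SAP 15.1: "The primary analysis will be performed separately for age groups for the PAS".
- SAP 15.1.3 applies the decision rule to the whole Primary Analysis Set (PAS) and adds: "Primary analysis will be also repeated by age groups".
- Protocol 5.2 doubles 60 to 120 because "the primary endpoint will be analysed separately for the 2 age groups".

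**The concern.** An imputation model should contain the terms that the later analysis estimates. Here that analysis includes the arm difference within each age stratum. A model with arm and age but no product of the two fits one arm difference for all ages. Imputed children in both strata then carry an average effect, and splitting the completed data by stratum cannot restore the stratum's own effect.

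Direction matters in an equivalence trial. In a stratum where stopping pants makes a real difference, the imputed estimate is drawn inwards, towards the equivalence region. In the other stratum it is pushed outwards, which makes true equivalence harder to show.

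**Working it through.** **Inputs from the documents.** Wet-night probabilities are 0.95 (continue) and 0.80 (stop), so the planned difference is 0.15. The margin is 2/7 = 0.286, read here as a proportion (two nights in seven). Allocation is 2:1. Each age group needs 15 + 30 children and is raised to 60. The rule is a two-sided 95% CI inside ±2/7 (Protocol 5.1, 5.2; SAP 8.1).

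**Assumptions.** The effect gap between age groups, the completely-at-random missingness and any within-child correlation are assumed; the documents give none of them. The run-in average is left out because eligibility makes it nearly constant.

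**The plan's own figure.** Binomial(7, p) counts for 15 versus 30 children, 20,000 replicates, give 97.7% power with a Wald 95% CI, against the stated 99%. That is close enough, and nothing below depends on it.

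**Formula.** With share f missing and equal-sized groups with true effects d1 and d2, group 1's imputed estimate is about

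(1 − f)·d1 + f·(d1 + d2)/2 = d1 − f·(d1 − d2)/2.

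- Gap 0.15, f = 0.20: 0.20 × 0.075 = 0.015; × 7 = 0.105 night per week.
- Gap 0.286 − 0.014 = 0.272, f = 0.20: 0.20 × 0.136 = 0.027; × 7 = 0.19 night. As a share of that group's true effect, 0.027/0.286 is about 9%.

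**Simulation, 20 + 40 per age group** (1,500 trials, 30 imputations, Rubin's rules). True effects are 0.286 and 0.014. False equivalence is for the group at the margin; the nominal rate is 2.5%.

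| Missing | Estimates, listed terms | False equivalence, independent nights: listed / with interaction | Same, within-child correlation 0.2 |
|---|---|---|---|
| 20% | 0.259, 0.042 | 4.7% / 1.2% | 2.9% / 1.1% |
| 30% | 0.244, 0.057 | 7.7% / 1.5% | 4.9% / 1.4% |
| 40% | 0.230, 0.070 | 13.3% / 1.7% | 6.0% / 1.9% |

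With the interaction, the estimates return to 0.286 and 0.014. Repeat runs give 8–9% at 30% missing with independent nights, and 2.6–3.6% at 20% missing with correlation 0.2. The Monte Carlo standard error at 2.5% is √(0.025 × 0.975/1500) = 0.4 points, so 2.9% cannot be told apart from nominal.

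**Simulation, 15 + 30 per age group** (20 imputations):
- True 0.00 and 0.15: the listed terms give 0.014 and 0.133 at 20% missing, 0.030 and 0.119 at 40%. The interaction model gives 0.000 and 0.150 at 20%.
- True 0.00 and 0.286: false equivalence is 3.6%, 5.8% and 10.2% at 20%, 30% and 40% missing, against 1.9%, 1.5% and 2.0% with the interaction.
- True 0.15 in both: no systematic shift.
- The whole-set estimate barely moves (0.073 against 0.075 for true 0.00 and 0.15 at 20% missing).

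**Smaller gap, one group still at 2/7.** With a gap of 0.15 and 20 + 40 per group, false equivalence under the listed terms is 1.7–1.8% at 20% missing and 2.3–2.6% at 30%. With correlation 0.2 it is 1.2% and 1.5%. With 15 + 30 and true effects 0.15 and 0.286, the group truly at 0.15 is pushed outwards: equivalence is declared in 69.4% of trials at 20% missing, against 79.8% with the interaction.

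**The case against.** **Imputation is mostly described as a sensitivity analysis.** Protocol 5.4.5 and SAP 8.3 analyse observed values, make imputation optional and set it beside the complete-case result. SAP 15.1.4 labels it a sensitivity analysis. Only SAP 15.1.2 reads as if it were the main method. This stands. A reader might infer that the trial's main conclusion is biased towards equivalence; the documents do not support that. The complete-case result does not use this model and is unbiased under the missingness assumed here.

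**The age-group result may not be the primary one.** SAP 15.1.3 and Protocol 5.4.2 apply the rule to the whole set, the protocol synopsis then presents results by age, and SAP 8.4 calls these subgroup analyses. SAP 15.1 and Protocol 5.2 point the other way. The conflict needs resolving, but on either reading an equivalence result per age group is produced.

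**The list may not be the full specification.** SAP 15.1.2 says which variables the model will include, not its functional form. That is fair, but PROC MI adds no interaction unless told to, so following the text as written leaves it out.

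**The inflated error rates need an extreme gap.** This also stands. Protocol 5.2 uses one pair of rates for both groups, and nothing in the documents suggests that the effect varies by age. A reader might also infer that between-group differences shrink by at least 20% whenever imputation runs. The trigger is not stated per age group, so one group could have much less missing.

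**Conclusion.** The point holds, conditionally. As listed, the imputation model does not match the age-group comparison that it feeds. Bias arises only if imputation is triggered and the arm effect truly differs by age, and it is confined to the imputed age-group results.

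The shift is modest at the trigger: 0.1 to 0.19 night per week for gaps of 0.15 to 0.27, growing with missingness. False equivalence stays at about the nominal level for a gap of 0.15 at 20–30% missing. For a gap of 0.27 with independent nights it reaches about 5% at 20% missing and 8–9% at 30%; with within-child correlation 0.2 it is about 2.6–3.6% at 20%. All of this rests on assumed gaps, completely-at-random missingness and the margin read as two nights in seven.

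It is still worth correcting. Protocol 5.4.6 itself warns of substantial missing diary data, and a sensitivity analysis that narrows the difference between age groups by construction is a poor check on the age-group results.

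**What to change.** In SAP 15.1.2, add the randomisation age stratum and its interaction with randomisation group to the imputation model (for example, PROC MI with FCS or monotone regression), or run PROC MI by age stratum. Use these data sets for the age-group comparisons. In the same edit, state whether imputation is the main or a sensitivity method, so that 15.1.2 agrees with 8.3 and 15.1.4, and reconcile 15.1 with 15.1.3 on which comparison is primary.

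No new data are needed. The cost is some precision when effects are in fact equal. With 0.15 in both groups, 20 + 40 per group and independent nights, age-group power in the imputed analysis falls from 95.2% to 92.9% at 20% missing and from 91.2% to 86.0% at 30%. That is about 2 and 5 points, down to roughly complete-case power (93.6% and 86.4%). With 15 + 30 per group, the loss is about 4 points at 20% missing (87.1% to 83.3% in one group, 85.5% to 81.3% in the other).
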